5.1. Handling of Missing Neuro Assessment Data at the Final Analysis

All efforts will be put forth to ensure near complete follow-up is obtained, in particular with the assessment of the primary outcome (mRS at 90 days). The final analysis will be conducted when all subjects have reached the upper limit of the window for the 90-day follow-up window (105 days after index procedure), and when the study sites believe they have exhausted all reasonable efforts to obtain outcome data collected within the window.

Nevertheless, some missing data may result. Missing 90-day mRS data (no mRS available within a 75-105 day window) will be handled by imputing the 30-Day mRS. In the case of patient death prior to the completion of the 90-Day visit, the subject will be counted as a failure (mRS = 6).

Missing 90-day NIHSS data (no NIHSS available within a 75–105-day window) will be handled by imputing the 30-Day NIHSS. In the case of missed 30-day NIHSS or of potential death prior to the completion of the 90-Day visit, the last study reported NIHSS will be imputed for analysis.

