11.2 Day 5-7 or Discharge

The patient may be discharged from the hospital when clinically stable, at the Investigator's discretion. The following neurological assessments must be obtained between Day 5-7 (if patient remains in hospital) or prior to discharge, whichever is earlier:

- NIH Stroke Scale
- Modified Rankin Scale

The neurological assessment must be performed whether or not it is considered part of the Investigator's standard of care and must be performed by neurologist or NIHSS-certified personnel. Every attempt should be made to have the same person conduct the exam at each follow-up visit. This assessor should be independent of the treating operator and patient's mechanical neurothrombectomy procedures. The primary operator of the treated patient may not perform the neurological exam.

Records of any changes to the patient's study medications are to be recorded from the 24-hour post-op visit up to discharge. All Adverse Events occurring from the 24-hour post-op visit to patient discharge are to be reported. In the case of a suspected neurological event, NIHSS should be repeated as close to and prior to the 24th hour of symptom onset.

In the event of patient death prior to the 5-7 day or discharge assessment, all available information regarding the primary cause of death and date/time of death will be reported. Additionally, site will report if the patient had "do not resuscitate" (DNR) or "comfort care only" status prior to expiration. All deaths must be reported to Sponsor within 24 hours of becoming aware (as per section 12).

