11.3 Clinical Follow-up

Trained study staff at each site will review the study requirements with the patient to maximize compliance with the follow-up schedule. The trained study staff will instruct patient to return for follow-up assessments according to the study schedule of events listed in Appendix 1.

11.3.1 30 Days

The following neurological assessments must be obtained 30 days (+/- 7 days) from the index procedure:

- NIH Stroke Scale (required only for in office visits)
- Modified Rankin Scale

This visit may be completed via phone or in office visit. If a phone visit is administered, then the NIHSS will not be completed. If an in-office visit is completed both the NIHSS and mRS assessments should be completed. This visit and associated neurological assessments must be performed whether or not they are considered part of the Investigator's standard of care and must be performed by neurologist or NIHSS-certified personnel. Every attempt should be made to have the same person conduct the exam at each follow-up visit. This assessor should be independent of the treating operator and patient's mechanical neurothrombectomy procedures. The primary operator of the treated patient may not perform the neurological exam.

Records of any changes to the patient's study medications are to be recorded from discharge up to the 30-day follow-up visit. All Adverse Events occurring from discharge to the 30-day follow-up visit are to be reported. In the case of a suspected neurological event, NIHSS should be repeated as close to and prior to 24th hour of symptom onset.

In the event of patient death prior to the 30-day assessment, all available information regarding the primary cause of death and date/time of death will be reported. Additionally, site will report if the patient had "do not resuscitate" (DNR) or "comfort care only" status prior to expiration. All deaths must be reported to Sponsor within 24 hours of becoming aware (as per section 12).

11.3.2 90 Days

The following neurological assessments must be obtained 90 days (+/- 14 days) from the index procedure:

- NIH Stroke Scale
- Modified Rankin Scale

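### The SAP's missing-data rule for the 90-day mRS replaces real scores obtained just outside the window with the day-30 score, leaves patients with neither score undefined, and uses a window one day wider at each end than the protocol's

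*SAP*

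**What the plan says.** Protocol 11.3.2 requires: "The following neurological assessments must be obtained 90 days (+/- 14 days) from the index procedure". The Schedule of Events in Protocol Appendix 1 gives the same ± 14 days.

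SAP 5.1 places the upper limit of the 90-day window at "105 days after index procedure" and then sets the rule for the mRS: "Missing 90-day mRS data (no mRS available within a 75-105 day window) will be handled by imputing the 30-Day mRS". For a death before the 90-day visit, "the subject will be counted as a failure (mRS = 6)".

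For the NIHSS, SAP 5.1 uses the same 75 to 105 day window and the same day-30 substitution, and adds a further step. If the day-30 value is also missing, "the last study reported NIHSS will be imputed for analysis". The mRS has no such step, although Protocol 11.2 collects an mRS at Day 5-7 or discharge.

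SAP 9.1.1.1 defines the outcome as the proportion of NITE 1 patients with mRS 0-2 at 90 days and does not say how a patient without a value is counted. The all-subjects denominator in SAP 8 is stated for safety events only. SAP 2 and 4 and Protocol 14.3 undertake to include all available ITT data. No sensitivity analysis of the mRS is named; SAP 2 only allows unspecified exploratory analyses.

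**The concern.** Three things need attention, in rising order of importance.

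- **Window.** A score on day 75 or day 105 is a valid primary outcome under the SAP but outside the visit window of the protocol.
- **No rule for patients with neither score.** If a living patient has no in-window mRS and no day-30 mRS, the analyst must decide whether the patient counts as a failure or leaves the denominator. As written, that decision would be made with the data in view.
- **Real scores set aside.** Read literally, the rule discards an observed mRS from a living patient because it fell a day or more outside 75 to 105, and uses a score from about two months or more before day 90's neighbourhood closes. This applies to early as well as late scores, and it fits poorly with the undertaking to use all available ITT data.

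No hypothesis is tested (Protocol 14.3), so type I error and power are not at issue. The estimate itself is the result. SAP 5 sets it against a literature average for mRS 0-2 at 90 days, with as few as 30 patients in the PP population.

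**Working it through.** **1. The window.** Input: 90 ± 14 days (Protocol 11.3.2 and Appendix 1).

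- 90 − 14 = 76 and 90 + 14 = 104, against 75 and 105 in SAP 5.1.
- Half-width of the SAP window: (105 − 75) / 2 = 15 days, not 14.
- Counting the procedure as day 1 does not reconcile them: 91 − 14 = 77 and 91 + 14 = 105.

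The SAP figure is therefore not reproduced from the protocol. The gap is one day at each end, and the SAP window is the wider.

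**2. Age of the substituted score.** Input: "The following neurological assessments must be obtained 30 days (+/- 7 days) from the index procedure", so day 23 to 37.

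- Late example, score on day 106: 106 − 37 = 69 and 106 − 23 = 83. The substitute is 69 to 83 days older.
- Early example, score on day 74: 74 − 37 = 37 and 74 − 23 = 51. The substitute is 37 to 51 days older.

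**3. Weight of one patient.** If the day-30 score and the discarded score fall on opposite sides of the cut between 2 and 3, the proportion moves by 100 / N points. Inputs: PP target 30 to 40, ITT maximum 60 (Protocol 14.2).

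| N | One patient | Three patients, all in the same direction |
|---|---|---|
| 30 | 3.3 | 10.0 |
| 40 | 2.5 | 7.5 |
| 60 | 1.7 | 5.0 |

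**4. Patients with neither score.** The documents give no missing-data rate, so the inputs here are assumptions: N = 30, 3 living patients with neither score, and 8, 11 or 14 of the other 27 independent.

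| Independent of 27 | Three dropped | Three as failures | Three as successes | Dropped minus failures |
|---|---|---|---|---|
| 8 | 8/27 = 29.6% | 8/30 = 26.7% | 11/30 = 36.7% | 3.0 points |
| 11 | 11/27 = 40.7% | 11/30 = 36.7% | 14/30 = 46.7% | 4.1 points |
| 14 | 14/27 = 51.9% | 14/30 = 46.7% | 17/30 = 56.7% | 5.2 points |

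The full range from failure to success is 3/30 = 10 points in each row.

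**5. Scale.** At an assumed 12 of 30 (40.0%), the exact 95% interval runs from 22.7% to 59.4%.

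**The case against.** The case for leaving the rule alone has real content.

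- Every visit that complies with the protocol falls inside the SAP window, so the one-day mismatch alone will rarely change a result. This stands; it is a wording correction.
- Deaths before the 90-day visit are already failures, so the worst outcomes cannot drop out. This stands, and it confines the problem to living patients.
- The group affected should be small. The day-30 mRS may be taken by phone (Protocol 11.3.1), as may the day-90 mRS if COVID-19 prevents an on-site visit (Protocol 11.3.2). This is plausible, but SAP 5.1 itself expects some missing data.
- Sampling error is larger than any of these effects. True, but sampling error is unavoidable, whereas this discretion can be removed in a few sentences.
- The literature comparison is descriptive, and Listings 6.1 and 6.8 should let a reader trace the affected patients. Tracing them afterwards does not fix the rule beforehand.

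A reader might go further and infer that the SAP drops patients with neither score and so favours the device. The text does not say that. It gives no rule, and a proportion of NITE 1 patients can equally be read as keeping them in the denominator as non-successes. A reader might also infer a known direction of bias from the carry-forward. The documents do not support one: using day 30 understates independence if patients improve afterwards and overstates it if survivors worsen.

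**Conclusion.** The point holds as a gap worth closing before the final analysis; it does not show bias in a given direction. Two parts rest on the text alone: the windows conflict by one day at each end, and the literal rule overrides a living patient's observed out-of-window mRS with a day-30 score, with no alternative analysis named. The third part is an omission: living patients with neither score have no stated handling and no stated denominator.

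The size per patient (3.3, 2.5 or 1.7 points at N = 30, 40 or 60) is arithmetic. The illustration that dropping three such patients, rather than counting them as failures, raises the result by about 3 to 5 points depends on the assumed three of 30 and on the assumed 8 to 14 independent of 27. With complete follow-up the effect would be nil.

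**What to change.** In SAP 5.1, and in the protocol where needed:

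1. Use one 90-day window in both documents, for the mRS and the NIHSS alike.
2. If a living patient has no in-window mRS, use the observed mRS nearest day 90 within a pre-stated outer limit, whether before or after the window. Fall back to day 30 only if there is none.
3. Count a living patient with no usable score as not independent, and state whether the Day 5-7 or discharge mRS can ever count as usable. Keep deaths at mRS 6.
4. Fix the denominator at all patients in each analysis population, ITT and PP.
5. Beside the main result, report three rows: observed cases (in-window scores and deaths only), every living patient without an in-window score as a failure, and the same patients as successes.

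The cost is a few sentences, three table rows and a slightly wider spread of assessment times for a few patients; no new visits are required. Because SAP 5.1 ties the final analysis to day 105, that trigger must be adjusted if the outer limit lies beyond it.

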9.2 Patient discontinuation

Where possible, every effort should be made for a patient to remain in the study until completion of the required follow-up period. However, if needed the patient's participation in the study may be discontinued at any time during the study. If this occurs, the reason for discontinuation should be documented in the source documentation, and the appropriate Case Report Form (CRF) must be completed. Factors leading to patient discontinuation may include, but are not limited to the following:

- **Patient Withdrawal:** Patient participation in a clinical trial is voluntary and the patient may discontinue participation (refuse all subsequent testing and follow-up) or withdraw their consent from the study at any time without affecting their future medical treatment or benefits.
- **Investigator Termination:** The Investigator may terminate the patient's participation without regard to the patient's consent if the Investigator believes it is medically necessary.
- **Lost to Follow-up:** A patient will be considered lost to follow-up after three unsuccessful, documented attempts have been made to contact the patient.
- **Death of Patient:** Upon notification of the death of the patient, the study site will be responsible for notifying Sponsor within 24 hours (refer to Section 12.2):

10 Study Procedures

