12.2 Serious Adverse Events

When an adverse event meets the definition for serious adverse event, it should be considered as such and reported immediately (within 24 hours) of becoming aware of the event to the Sponsor and recorded in the source documentation. The SAE should be further reported to the reviewing IRB per hospital IRB requirements. An adverse event is considered serious if the event:

- Leads to death;
- Leads to a serious deterioration in the health of the patient that:
 - Results in life-threatening illness or injury;
 - Results in permanent impairment of a body structure or a body function;
 - Requires inpatient hospitalization or prolongation of existing hospitalization;
 - Results in medical or surgical intervention to prevent permanent impairment to a body structure or a body function.

An Adverse Event form will be completed promptly and no later than 10 working days after becoming aware of the event. Reports relating to the patient’s subsequent medical course must be submitted to the Sponsor and the reviewing IRB until the event has subsided or, in case of permanent impairment, until the event has stabilized, and the overall clinical outcome has been ascertained.

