9.1.1.2. Summary of Neurologic Assessment at 90 days

The summary of neurological assessments at 90 days is defined as the proportion of NITE 1 patients with a nondisabling or disabling stroke according to the NIHSS and will be presented in Table 6.9 entitled *Summary of Neurological Assessment at 90 days*. An NIHSS of ≤ 4 is indicative of a nondisabling stroke and an NIHSS ≥ 5 will be evaluated as a disabling stroke. Listing 6.9 entitled *NIH Stroke Scales (NIHSS)* supports Table 6.9.

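### SAP 5.1 carries a dead patient's last NIHSS forward to day 90, so a death with a last score of 0–4 is tabulated as a nondisabling stroke

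*SAP*

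**What the plan says.** SAP 5.1 sets separate rules for the two 90-day neurological scales.

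- **mRS.** If the patient dies before the 90-day visit, "the subject will be counted as a failure (mRS = 6").
- **NIHSS.** A missing 90-day score is replaced by the 30-day score. If the 30-day score was missed, or in the case of "potential death prior to the completion of the 90-Day visit, the last study reported NIHSS will be imputed for analysis".

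SAP 9.1.1.2 defines how the 90-day NIHSS is reported in Table 6.9: "An NIHSS of ≤ 4 is indicative of a nondisabling stroke and an NIHSS ≥ 5 will be evaluated as a disabling stroke". It names no category for death and makes no exception for imputed scores.

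The Protocol determines which score can be the last one:

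- Section 8.4, criterion 4b, excludes patients with an NIHSS of 5 or less, so the lowest eligible baseline score is 6.
- Section 11.1 requires an NIHSS at 24 hours (± 6 hours).
- Section 11.2 requires the next one early: "The following neurological assessments must be obtained between Day 5-7 (if patient remains in hospital) or prior to discharge, whichever is earlier".
- Section 11.3.1 allows the 30-day visit by telephone: "If a phone visit is administered, then the NIHSS will not be completed".
- Section 11.3 also provides for unscheduled scores: "In the case of a suspected neurological event, NIHSS should be repeated".

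**The concern.** Death before day 90 is a known outcome and not a missing score. The NIHSS in Protocol Appendix 2 runs from 0 to 42 and has no value for death, so carrying a score forward gives a dead patient a 90-day neurological status that never existed. If that score is 4 or less, the patient enters the favourable row of Table 6.9.

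Two outputs of the same report then disagree about one patient: mRS 6 in the data behind Table 6.8, and nondisabling in Table 6.9. What is at stake is the proportion printed in Table 6.9. SAP section 2 says the planned analyses may be used in regulatory submissions, presentations and manuscripts, where that proportion could be quoted without the listings that show the deaths.

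**Working it through.** The plan states no figure to reproduce here. Protocol 14.3 says no formal hypothesis is tested. The check applies the two SAP rules in sequence and then sizes the effect.

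**Step 1: classify a death by its last score (SAP 5.1, then SAP 9.1.1.2).**

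| Last recorded NIHSS before death | Row in Table 6.9 | mRS under SAP 5.1 |
|---|---|---|
| 0, 1, 2, 3 or 4 | nondisabling | 6 (failure) |
| 5 or more | disabling | 6 (failure) |
| Baseline only (at least 6) | disabling | 6 (failure) |

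Only a post-procedure score can place a death in the nondisabling row.

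**Step 2: can a score of 0–4 be the last one?** Yes. A patient may improve to 4 or less by the Day 5–7/discharge assessment, have a telephone visit at 30 days with no NIHSS, and then die with no suspected neurological event to prompt a repeat. The Day 5–7/discharge score is taken no later than Day 7, which is at least 90 − 7 = 83 days before the time point it is reported under.

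**Step 3: size per death.** Deaths stay in the denominator N both under the present rule and under the proposed one. With k deaths whose last NIHSS is 0–4, the nondisabling proportion differs by k/N. The values of N come from Protocol 14.2.

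| N | k = 1 | k = 2 |
|---|---|---|
| 30 (PP minimum) | 1/30 = 3.3 points | 2/30 = 6.7 points |
| 40 (PP maximum) | 1/40 = 2.5 points | 2/40 = 5.0 points |
| 60 (ITT maximum) | 1/60 = 1.7 points | 2/60 = 3.3 points |

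**Step 4: illustration with assumed counts.** Take N = 30, with 12 survivors nondisabling, 12 survivors disabling and 6 deaths, of which 2 had a last score of 0–4.

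- SAP rule: nondisabling (12 + 2)/30 = 46.7%; disabling (12 + 4)/30 = 53.3%.
- Deaths in their own row: nondisabling 12/30 = 40.0%; disabling 12/30 = 40.0%; dead 6/30 = 20.0%.

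**Step 5: assumed range.** The documents give neither the expected mortality nor the share of deaths with a last score of 0–4. If each lay between 10% and 30%, the expected excess would run from 0.10 × 0.10 = 1 point to 0.30 × 0.30 = 9 points at any N. These inputs are assumptions and not trial figures.

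**The case against.** **The scales differ.** The mRS has a level for death and the NIHSS does not, so SAP 5.1 had to treat them differently. The last measured deficit could be read as stroke severity while alive, with death captured by the mRS and the adverse event tables. The first half is right: the difference between the two rules is not by itself an error. The second half fails because the endpoint is labelled as an assessment at 90 days. The lack of a death value on the NIHSS is the reason to report death separately.

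**The reach is narrow.** The patient must improve from at least 6 to 4 or less and then die with no later, higher score. Repeat scoring after suspected neurological events leaves mainly sudden or non-neurological deaths. This stands. It limits the likely count and does not change the rule.

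**Deaths are visible elsewhere.** They appear in the disposition listing (SAP 6.1), in the serious adverse event outputs (SAP 8.2; Protocol 12.2 counts an event as serious if it "Leads to death") and as mRS 6 in Listing 6.8. With at most 60 patients, a reader could match Listing 6.8 against Listing 6.9. This also stands, but none of it corrects the proportion in Table 6.9.

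**The age of the score.** For a patient who died, the relevant gap runs from the last score to death, not to day 90. That is fair. The 83 days show only how far a carried score can lie from its reported time point, and the conclusion does not depend on them.

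**The word *potential* before death.** If it meant only unconfirmed death, a confirmed death would still have no NIHSS in the 90-day window and would fall under the general rule: the 30-day score or, failing that, the last one. Either reading carries a pre-death score forward.

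**Conclusion.** The concern holds. Under SAP 5.1 and 9.1.1.2 as written, a death before the 90-day visit with a last NIHSS of 0–4 is counted as a nondisabling stroke at 90 days, and no other section overrides this. Compared with counting no death as nondisabling, the rule can only raise that proportion: by 3.3, 2.5 or 1.7 points per such death at N = 30, 40 or 60, with all patients in the denominator. Deaths with a last score of 5 or more leave the nondisabling proportion unchanged but are shown as disabling strokes and not as deaths.

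The consequence is limited. The endpoint is secondary and descriptive, has no planned comparison in SAP Table 1, and does not affect the primary mRS result. It should still be corrected, because the stated rule gives a wrong proportion and the remedy is cheap.

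**What to change.** - **SAP 5.1:** remove known deaths before the 90-day visit from the NIHSS carry-forward. Keep the existing rule for other missing scores, including patients lost to follow-up under Protocol 9.2 ("A patient will be considered lost to follow-up after three unsuccessful, documented attempts have been made to contact the patient"). Replace the wording about potential death so that it is clear which patients are meant.
- **SAP 9.1.1.2 and Table 6.9:** add a row for death before the 90-day visit, keep these patients in the denominator, and count none of them as nondisabling.
- **Optional:** show observed 90-day scores only, beside the imputed display.

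The cost is a change of SAP wording and one table row. No new data are needed, since deaths are already recorded. The nondisabling proportion may come out slightly lower, and deaths with a last score of 5 or more move from the disabling row to the death row.

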This visit is expected to be completed as an in-office visit. The neurological assessment must be performed whether or not it is considered part of the Investigator's standard of care and must be performed by neurologist or NIHSS-certified personnel. Every attempt should be made to have the same person conduct the exam at each follow-up visit. This assessor should be independent of the treating operator and the patient's mechanical neurothrombectomy procedures. The primary operator of the treated patient may not perform the neurological exam.

Records of any changes to the patient's study medications are to be recorded from the 30-day follow-up call/visit up to the 90-day follow-up visit. All Adverse Events occurring from the 30-day follow-up call/visit to the 90-day follow-up visit are to be reported. In the case of a suspected neurological event, NIHSS should be repeated as close to and prior to 24th hour of symptom onset.

In the event of patient death prior to the 90-day assessment, all available information regarding the primary cause of death and date/time of death will be reported. Additionally, site will report if the patient had "do not resuscitate" (DNR) or "comfort care only" status prior to expiration. All deaths must be reported to Sponsor within 24 hours of becoming aware (as per section 12).

If the COVID-19 Pandemic impacts the ability of the patient or site to complete this visit on-site, a remote phone visit may be done. If a phone visit is administered, then the NIHSS will not be completed.

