20.2 Visits/Procedures

A site's ability to conduct follow-up visits on-site may be impacted due to the pandemic. In these circumstances the site should make efforts to conduct e-visits (phone/ video based) within study visit windows. If e-visits are implemented, the site will ensure:

- Trained study staff conducting e-visits have been trained on how to conduct e-visits (e.g., training on the use of telemedicine applications).
- Procedures to maintain patient's privacy are in place, as would be done for an on-site clinical visit.
- Both the investigator and the trial participant should confirm their respective identities with one another before engaging in a real-time video conference visit according to an identity verification plan developed by the sponsor.

It is understood that the use of e-visits will limit the ability of trained study staff to complete all protocol required neurological assessments. The NIHSS will not be collected at these e-visits.

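### When the 90-day and 30-day NIHSS are both missing, SAP 5.1 carries forward a score of any age, so a living patient's first-week score can be reported as the 90-day result

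*SAP*

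**What the plan says.** SAP section 5.1 sets two steps for a 90-day NIHSS that is missing from its 75 to 105 day window. First, the gap "will be handled by imputing the 30-Day NIHSS". Second, if the 30-day score was also missed, or the patient may have died before the 90-day visit, "the last study reported NIHSS will be imputed for analysis".

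The protocol decides which scores exist:

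- **30 days (section 11.3.1).** "This visit may be completed via phone or in office visit. If a phone visit is administered, then the NIHSS will not be completed". The choice is open to any patient and does not depend on the pandemic.
- **90 days (section 11.3.2).** "This visit is expected to be completed as an in-office visit". A phone visit without NIHSS is allowed if COVID-19 prevents attendance. Section 20.2 says the same of remote visits in general: "The NIHSS will not be collected at these e-visits".
- **Before 30 days (sections 10.2, 11.1 and 11.2).** NIHSS is scheduled at baseline, at 24 hours, and at day 5-7 or discharge, whichever is earlier.
- **Unscheduled (sections 11.1 to 11.3.2).** NIHSS is to be repeated after a suspected neurological event.

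SAP section 9.1.1.2 takes the resulting value into Table 6.9. A score of 4 or less is "indicative of a nondisabling stroke", and 5 or more counts as disabling.

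**The concern.** The first fallback for NIHSS depends on an assessment that the protocol makes optional. Once it is absent, the second fallback reaches back into the first week after the stroke and presents what it finds as a 90-day result. Exclusion criterion 4b removes patients with NIHSS of 5 or less, so every eligible patient starts on the disabling side of the 4/5 cut. Whether a patient has crossed it by day 90 is what the endpoint is meant to show, and a score from day 7 or earlier cannot show that.

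A patient who recovers after discharge would be tabulated as disabled. One who leaves hospital with a score of 4 or less and declines without a recognised event would be tabulated as nondisabled. Neither document limits the age of the carried score, plans a sensitivity analysis for it, or says that imputed values will be marked. Because the study tests no hypothesis (protocol section 14.3), the descriptive proportions are its results, and their labels should be accurate.

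**Working it through.** The documents give no missing-data rate for NIHSS and no target for this endpoint, so there is no planned figure to reproduce. The check has two parts.

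**1. Trace the rule through the visit schedule for a living patient.**

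- 90-day NIHSS present: it is used, and a 30-day phone visit does no harm.
- 90-day missing, 30-day in-office score present: the 30-day score is used.
- Both missing: the last reported score is used. This is normally the day 5-7 or discharge score. It is the 24-hour score only if the discharge score is also absent, and a later score if one was taken after a suspected event.

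A score from day 7 or earlier is at least 90 − 7 = 83 days old at day 90.

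For comparison, the mRS rule in SAP section 5.1 names only the 30-day value for living patients. The 30-day mRS is taken by phone or in the office, so that fallback works. NIHSS, whose 30-day fallback is less reliable, has the looser rule.

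**2. Scale.** Population sizes come from protocol section 14.2: 30 to 40 per protocol, at most 60 intent-to-treat. The rates are assumptions:

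- a = share of 30-day visits done by phone, 25-75%
- b = share of 90-day NIHSS missing, 5-20%
- c = share of affected patients who cross the 4/5 cut between the carried score and day 90, 20-40%

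With a and b independent, the share with both missing is a × b: 0.25 × 0.05 = 1.25%, up to 0.75 × 0.20 = 15%. One misclassified patient moves the proportion by 100/n points. The expected number affected is n × a × b, and the chance of at least one is 1 − (1 − ab)^n.

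| n | Points per patient | Expected number affected | Chance of at least one |
|---|---|---|---|
| 30 | 3.3 | 0.4 to 4.5 | 31% to 99% |
| 40 | 2.5 | 0.5 to 6.0 | 40% to over 99% |
| 60 | 1.7 | 0.75 to 9.0 | 53% to over 99% |

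The gross shift is a × b × c: 0.0125 × 0.20 = 0.25 points, up to 0.15 × 0.40 = 6 points. This counts every crossing in the same direction. If some go each way they cancel, and the net shift can be zero.

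Independence matters. If every patient without a 90-day NIHSS had also done day 30 by phone, the share with both missing would be b itself, 5-20%, and the gross shift 0.05 × 0.20 = 1 point up to 0.20 × 0.40 = 8 points.

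**The case against.** The strongest case against is that the route is narrow and the stakes are low. Two assessments must be missing. The 90-day visit is an office visit by default, patients who cannot return should not be enrolled (protocol section 8.1 and inclusion criterion 6), and the SAP expects sites to pursue outcome data fully. A recognised late deterioration should produce a repeat NIHSS, which then becomes the last reported score, so unrecorded recovery is the stronger half of the concern. The endpoint is secondary, has no comparator in SAP Table 1, and sits beside a primary mRS outcome that can still be recorded remotely. Listing 6.9 will show NIHSS data. All of this stands, and it limits the size and rank of the point. It does not remove the rule: no age limit is set, and the listing is not said to identify carried values.

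A reader might infer more than the documents support:

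- **That any phone visit puts an acute score into the 90-day table.** It does not. The 90-day score must be missing first, and the 90-day phone visit is only a COVID-19 contingency, although an ordinary missed visit triggers the same rule.
- **That the 24-hour score is the usual substitute.** It is used only if the mandatory day 5-7 or discharge score is absent and no later score exists.
- **That the result is biased in a known direction, or by a known amount.** Improvement after discharge would overstate disabling stroke and later decline would understate it. The documents give no rates for either.

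**Conclusion.** The point holds in a limited form. In living patients with neither a 90-day nor a 30-day NIHSS, the stated rule can report a first-week score as a 90-day classification, and nothing in the plan makes this visible in Table 6.9. The certain part of the size is the weight of one patient: 3.3 points at n=30, 2.5 at n=40 and 1.7 at n=60. The gross shift of about 0.25 to 6 points rests wholly on the assumed rates and on independence of the two missing visits, and the net shift would be smaller if crossings go both ways. No hypothesis test, power or primary outcome is affected. It is worth correcting because the remedy is cheap and the SAP already stops at day 30 for mRS in living patients.

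**What to change.** Amend SAP section 5.1 and the Table 6.9 and Listing 6.9 specifications:

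- For living patients, carry forward to day 90 only an NIHSS taken in the 30-day window or later (day 23 onward, from 30 − 7). Do not use a 24-hour or day 5-7/discharge score.
- Show living patients without such a score as not assessed. Report the observed-only proportion, plus bounds that count all of them as nondisabling and then all as disabling, stating each denominator.
- Give patients who died before the 90-day visit their own row. The present sentence covers deaths as well, so restricting carry-forward without this row would leave early deaths with no rule.
- In Listing 6.9, flag each carried value with its assessment day.

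The cost is SAP wording and a few table rows, with no new visits or data. The downside is that a few patients become unclassified: 0.4 to 4.5 expected at n=30 under the assumed independent rates, which makes the bounds 1.25 to 15 points wide. An event-triggered score from before day 23 would no longer be carried forward, though it would still appear in the listing.
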